dangerously high. If participants decline to have 911 called, they will be required to sign a waiver indicating this decision. Participants will be advised to seek medical care immediately. Research Electronic Data Capture (REDCap), a secure, HIPAA-compliant web application for managing online surveys and databases, will be used to administer questionnaires. For participants who are eligible, study staff will describe the study and obtain informed consent. Participants will complete questionnaires on a laptop/tablet device, provide anthropometric measures, complete the fitness measures. Anthropometric measures include measured height, weight, waist circumference, and percent body fat. Height and weight will be measured using a stadiometer and digital scale, respectively. During the baseline assessment, study staff will work with participants to create a Fitbit account.

Process Evaluation. Process evaluation will be used to monitor and document program implementation via assessment of intervention dose (amount of intervention delivered and received), reach (extent of intervention participation by the target population), and fidelity (extent to which the intervention was implemented as planned). For dose, we will track the extent to which coaching session was completed, intended content was covered, and newsletters were received and read. Reach will be assessed by tracking participation of dyad members for each session (0, 1, or both) along with barriers to participation, dyad interaction, and use of the Fitbit, including frequency of monitoring partner's PA. Individual participants' Fitbit data from Fitabase dashboard will be used by intervention coaches to review participants' data and aid them with providing feedback. We will also use this information to evaluate participants' adherence to self-monitoring. To assess fidelity, all coaching sessions will be digitally recorded. Holistic nurse health coach will be required to keep detailed implementation logs showing the date and start and end times of sessions, individuals present, the content discussed, goals set by participants that will be followed up on the next session, dyad support plans, and any qualitative observations.

Measures: Surveys will be administered using Research Electronic Data Capture (REDCap), a secure, HIPAA- compliant web application. Table 1 (Appendix-D) shows the schedule of study procedures and constructs to be assessed, proposed measures, and the timing of assessment.

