primarily non-personal. Minimal risk is defined as the probability and magnitude of physical or psychological harm that does not exceed that encountered in ordinary, everyday life or in the performance of routine medical or psychological examinations. Risks include: becoming fatigued when participating in sessions, feeling uncomfortable interacting with the study team during sessions, and breach of confidentiality. Participants will be notified of these risks during the informed consent process. If any concerns arise during study procedures, participants will be reminded that participation is voluntary and they may refuse to answer any questions, end the session, or withdraw from the study at any time without fear of repercussion. If a participant is too tired or ill to continue with a scheduled session, the session will be ended and if (and only if) the participant is willing and able the session will be rescheduled. All attempts possible will be made to minimize the risk that a participant's data will become known to others outside the approved research team (see Data Management). The research team will ensure the anonymity of the participants by protecting personally identifiable information. The proposed study will be conducted in English; India is a linguistically diverse country with 22 languages recognized by the constitution of India¹¹⁷ and it is not feasible to conduct focus groups in multiple languages. However, English is also considered a popular second language in India¹¹⁸ and is used as the language for communication in U.S. Asian Indians speak English very well (57.7%)¹¹⁷ and limited English proficiency is fairly low (7.3%) and are bilingual since they speak another language at home¹¹⁷.

Height/Weight/Waistline Measurements

Having weight or waistline measurements taken may make participants feel uncomfortable. Participants may refuse to complete any procedure that makes them feel uncomfortable.

Physical Activity Side Effects

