This study encourages increased participation in physical activity of a moderate nature. This activity may result in mild physical discomfort (e.g., sore muscles, stiffness) for some participants. These effects have no long-term negative health implications and are a normal consequence of activity. However, more serious potential risks include pulled muscles, heart problems, chest tightness or discomfort, shortness of breath, and accidental injuries, such as falling. Possible outcomes could include referral to the participant's primary care physician and/or other physician. Our inclusion/exclusion criteria were designed to exclude participants who should not participate in regular light-to-moderate physical activity based on their responses to the PAR-Q and blood pressure measures without the authorization of a healthcare provider.

Study Withdrawal/Discontinuation

Participants may withdraw from this study at any point in time without repercussion, by simply indicating their desire to withdraw to a study team member.

Criteria for Removal from the Study:

- Participant or clinician request
- Inability to contact the patient for 1 month (up to 6 attempts will be made)
- Completion of study
- Study team determined the patient was no longer eligible

- Sessions were not productive
- Deceased
- Health status declined

All data captured from withdrawn participants will be considered evaluable and used for this study, unless a withdrawn participant requests to have their data destroyed.

Data and Safety Monitoring

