Study team members will continuously monitor participant safety and data quality whenever conducting study activities. Study personnel will maintain quality assurance procedures for all data. Survey data will be collected and managed using REDCap (Research Electronic Data Capture). All protected health information (PHI) will be removed from the data when it is exported from REDCap for analysis. Those having access to the data file include the study Principal Investigator (PI) and research team personnel and will monitor recruitment, data quality, data management, and human subjects' protection at least bi-weekly. Logs will be maintained of refusals during recruitment, any participant complaints, and other adverse events and will be reported according to Institution Review Board (IRB) requirements. [name] will work to address and resolve any concerns in the most expeditious manner possible. In particular, participant responses to recruitment attempts will be tracked in terms of methods of contact, and reasons for refusal (if available) and contact attempts made by the study team. This information will be reviewed on a bi-weekly basis, and if any concerning trends are noted in recruitment refusals, the IRBs will be notified and adjustments made to recruitment strategies and / or study procedures (as indicated).

Several procedures will be used to maintain the integrity of the data. Quality assurance procedures will include a data collection protocol documented in a protocol manual, and regular meetings among the investigators and project staff to review problems and solutions and discuss concerns. A specific audit trail system that identifies the date, time, and individual making changes on the database will be part of the data management system.

No protected health information will be included in the text/email messages (as there will be no health information in the message). Although participants' phone numbers and the content of the text messages will be disclosed to the automated text messaging service, no protected health information will be disclosed to the automated text messaging service. Participants will be informed that unencrypted text and email messages are not secure and may choose not to receive them.

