The feasibility of the intervention will be determined by comparing the percentages for overall recruitment and retention at week 12 to their target values of 80% and 70%, respectively. A secondary feasibility assessment will determine the proportion of intervention participants who take part in each of the intervention components (i.e., number of counseling calls completed, use of Fitbit, receipt and review of newsletters). In addition, every attempt will be made to query subjects lost to follow-up to ascertain the reason for drop out or barriers to participation. Feasibility will be measured by calculating the rates of enrollment, retention, assessment completion, and treatment adherence. The enrollment rate will be the proportion of those meeting inclusion criteria that enrolled, while the retention rate will be the proportion enrolled that complete the study. Assessment completion will be calculated as the proportion of assigned data collection forms that were completed. Treatment adherence will be calculated as the proportion of intervention sessions attended.

To explore trends in the outcomes data, means and standard deviations will be calculated for the instrument scores at baseline and week 12. As hypothesis testing is not the objective of a pilot

study¹¹⁸, these descriptive statistics will only be used to inform effect size estimation. Since the effect sizes in a pilot study may overestimate or underestimate the true effect sizes¹²⁰ the obtained effect size estimates will be considered in combination with clinically significant effect sizes for the outcome variables in determining the sample size for a future trial.

Power Analysis: The primary aims do not require power calculations given the focus on feasibility study.

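### The protocol promises an adverse event log but describes no systematic question about the exercise risks it names, so an empty log in 20 women would be hard to interpret

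*Combined protocol and SAP*

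**What the plan says.** Under Physical Activity Side Effects, the protocol accepts that the activity it encourages can cause more than sore muscles: "more serious potential risks include pulled muscles, heart problems, chest tightness or discomfort, shortness of breath, and accidental injuries, such as falling".

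Under Data and Safety Monitoring it makes two commitments. One is general: "Study team members will continuously monitor participant safety and data quality whenever conducting study activities". The other concerns records: "Logs will be maintained of refusals during recruitment, any participant complaints, and other adverse events". The log is to be reported as the IRB requires, and human subjects' protection is reviewed at least every two weeks. The section gives no definition of an adverse event, no question to ask, no recall period and no person responsible for asking.

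The regular contact is the coaching: six Zoom sessions per dyad of 45 minutes each, in alternate weeks. The Process Evaluation section requires the coach to log the date, the times and who attended, followed by "the content discussed, goals set by participants that will be followed up on the next session, dyad support plans, and any qualitative observations".

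For illness during a session, the section on risks and their minimisation says: "If a participant is too tired or ill to continue with a scheduled session, the session will be ended". The session is rescheduled if the woman is willing and able. The Study Withdrawal/Discontinuation section makes declining health a reason for removal. Neither event is tied to the adverse event log.

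The Statistics section names its measures: "Feasibility will be measured by calculating the rates of enrollment, retention, assessment completion, and treatment adherence". None of them is a measure of harm.

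**The concern.** The exercise takes place largely where no staff are present, and the coaching is remote. A fall, a strain or an episode of chest discomfort at home reaches the study only if someone mentions it or is asked. The protocol says where such an event would be written down, but not what would bring it to light.

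This matters for two reasons. First, the pilot is described under Anticipated Results and Potential for Extramural Funding as the basis for a larger efficacy trial and a grant application. The Background also says that heart attack and stroke tend to come earlier in this population. A statement that no events were recorded would be carried forward into that application, and readers could not tell whether women had been asked. Second, the gap cannot be repaired at analysis: an event that was never elicited leaves nothing to recover.

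**Working it through.** **Step 1: check each contact or instrument in the body text for a question about injuries, falls or exertional symptoms since baseline.**

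- *Coaching sessions (Dyad-based Zoom health coaching).* They cover progress, what worked and what did not, goals, problem solving and partner support. No symptom or injury question is described.
- *Coach's log (Process Evaluation).* It has no dedicated adverse event item. Two open entries, session content and qualitative observations, could hold one.
- *Private talks with the coach.* They are offered to each woman, in the context of difficulties between partners.
- *Call recordings.* They are kept to monitor coaching and for later evaluation. Review for harms is not mentioned.
- *Questionnaires.* The nearest is Health History, which asks about listed medical problems over the past 12 months. It does not cover falls or injuries, and at week 12 it could not separate events before baseline from events after it. The visit at which it is given is not stated.
- *Follow-up evaluation (Abstract).* It is open-ended and about satisfaction.
- *Women lost to follow-up (Statistics).* They are asked why they left, which may reveal a harm. Women who stay are not reached by this route.

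By contrast, Data and Safety Monitoring tracks recruitment refusals by method of contact, reason and number of attempts, and a worrying trend in refusals is the only stated trigger for notifying the IRBs and adjusting procedures.

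**Step 2: what an empty log would mean.** The plan gives no event rate, harm count or power figure, so there is nothing of its own to reproduce. What follows is illustration.

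Inputs: 10 dyads × 2 = 20 women (document). True 12-week risk *p* and capture fraction *c* are assumed. Women are treated as independent.

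Chance of recording no affected woman = (1 − *p*·*c*)^20. At *p* = 10%:

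| Capture *c* | Calculation | Chance of none recorded |
|---|---|---|
| 100% | 0.90^20 | 12% |
| 70% | 0.93^20 | 23% |
| 50% | 0.95^20 | 36% |
| 30% | 0.97^20 | 54% |

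At full capture, the chance of none recorded is 36% for *p* = 5% (0.95^20) and 1% for *p* = 20% (0.80^20). At half capture the figures are 60% (0.975^20) and 12% (0.90^20).

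**Step 3: the bound from zero events.** The one-sided 95% upper bound for 0/20 is 1 − 0.05^(1/20) = 13.9%. It bounds the risk of a *recorded* event. At half capture the same result is compatible with a true risk up to 0.139/0.5 = 27.8%, and at one quarter capture up to 0.139/0.25 = 55.6%. If only the women retained at the 70% target were asked, 20 × 0.70 = 14, and 0/14 gives 1 − 0.05^(1/14) = 19.3% even with full capture among them.

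**Step 4: independence.** Partners are encouraged to be active together, so their events may be correlated. Positive correlation raises the chance of recording none. In the extreme where partners always share the outcome, full capture at *p* = 10% gives 0.90^10 = 35% instead of 12%.

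**The case against.** A reader might infer that harms are captured only when a woman complains. The documents do not support that. The sentence on logs lists adverse events separately from complaints, safety monitoring is promised throughout study activities, and protection of participants is reviewed at least every two weeks. The coach's log has open entries, sessions discuss barriers and what did not work, calls are recorded, private talks are offered, and dropouts are asked why. The text is silent on method; it does not state a volunteered-only method. What remains is that none of these routes is directed at harms or applied to every woman, and a periodic review can examine only what was recorded.

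A reader might also infer that the pilot's harm count will be too low. That goes too far. No harm count is planned as an outcome, and the capture fraction is unknown. Under-recording is the likely direction, but neither its occurrence nor its size can be derived. The calculations show what assumed under-capture would do, not that it will happen.

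The absence of a week-12 question can be confirmed only for the body text. The schedule (Appendix D), the questionnaire table (Appendix E) and the protocol manual were not available, and this is not a fault of the plan. The body text does describe the Appendix E questionnaires briefly, and none of those described asks about injuries, falls or symptoms since baseline.

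Finally, this is a small feasibility study that the protocol describes as minimal risk, with PAR-Q and blood pressure screening at entry. Even perfect ascertainment of 0/20 leaves a bound of 13.9%. That limits how much the pilot can say about safety, and it is a reason to keep the remedy small. Screening reduces risk at entry but does not help detect an event afterwards.

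**Conclusion.** The point holds in a limited form. The text names serious exercise risks and promises a log, but describes no systematic question about those risks at the coaching sessions or at week 12, and no dedicated item in the coach's log. Events may be under-recorded by an amount the documents do not allow anyone to calculate, and no recorded events in 20 women should not be taken as evidence of safety.

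The contrast between 12% and 36% rests on an assumed 10% risk, assumed full or half capture, and independence between women. The conclusion rests on the body text alone and would fall away if the unavailable appendices or manual contain such a question. This is a worthwhile, inexpensive improvement to data collection and does not undermine the feasibility aims.

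**What to change.** 1. Add one standard item to the coach's log at each of the six sessions: any new symptom, injury, fall or medical visit since the last contact. Offer the existing private talk to any woman who prefers to answer alone. State who asks and who records.
2. Add the same item, covering the time since baseline, to the week-12 REDCap survey, which each woman completes individually.
3. Do not collect answers by text message. The coaching and Data and Safety Monitoring sections keep protected health information out of texts, and the latter says unencrypted messages are not secure.
4. Copy every positive answer, every session ended for illness and every removal for declining health to the adverse event log.
5. In the Statistics section, plan a descriptive summary: the number of women with any event, by type, out of those asked, with an exact interval. Note that a simple binomial interval ignores pairing within dyads.

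If Appendix D, Appendix E or the manual already contains such a question, a cross-reference covers that part, and the link to the log and the summary remain to be added.

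The cost is a log item, a survey item and a short table, using contacts already scheduled. The downside is a few minutes per session and a higher reported event count. What to do clinically about a positive answer is for the sponsor to decide.

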interviewing approach to promote social support between dyad members as they practice how to be supportive partners. Participants will be recruited by leveraging the PI's relationships with community- and faith-based organizations, through advertisement flyers, on-site recruitment, presentations during/before church services, social media, email list-serves, local SAI newspapers, health fairs, and health screenings targeting SAIs in Houston. Participants will be eligible for inclusion in the study if they satisfy all the inclusion criteria including inactive SAI women aged 40-65 years living in Houston, Texas. Participants will be assessed at baseline and immediately post-intervention. Physical activity will be assessed using self-reported and objective measures. Detailed screening log and record consent rates including refusal reasons, retention rates including attrition reasons, and completion of questionnaires will be tracked. We will also monitor session attendance, and participants will complete brief, open-ended evaluations of their overall satisfaction of the program at the follow up to determine intervention acceptability.

Background and Significance

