Recruitment: To facilitate sustainability, we will pilot this intervention with SAI women recruited from religious organizations. Faith is a significant component of many SAIs, and churches are an important element of SAI community. The Houston metropolitan area is home to many Asian Indian females in a close-knit community. According to the 2020 census data, Texas is one of the top three states in the U.S. with the largest number of Asian Indians (n=245,981, i.e., 0.9% of 25,145,561)⁸¹. The majority of the Asian Indian population resides in Houston (1.21% of 2,571,090), Stafford (7.35% of 27,677), Sugar Land (7.20% of 108,607), Missouri City (3.4% of 65,701), and surrounding neighborhoods of Houston⁸². The study will use purposive sampling of women who meet the study eligibility criteria. IRB approval will be obtained from the Committee for the Protection of Human Subjects (CPHS) at the University of Texas Health Science Center at Houston. Study participants will be recruited from Indian community churches that the PI used previously to successfully recruit the population of interest and we anticipate no challenges to recruiting for this study given previous experience and established contacts^{27,83}. Participants also will be recruited through advertisements through flyers (Appendix-A) on-site recruitment, presentations during/before church services, email list-serves, health fairs, and health screenings targeting Asian Indians in Houston. As the study progresses, snowball sampling may be employed in cases where a study participant wishes to recommend other Asian Indian women to ensure that the sample is not limited to those who are socially engaged and attend religious facilities.

Trained research staff will screen potentially eligible participants. Screening may be performed in person or over the phone. At this time, staff will explain the study, assess interest in participation, and for those interested, screen for inclusion/exclusion criteria. Determination of preliminary eligibility will be based on participants' self-reported responses to the screening

questions (Appendix -B). Participants will be informed that eligibility will be finalized with the measurement of blood pressure at the in-person baseline visit. Prospective participants will select their study partners. Screening of both dyad members is required prior to enrolling in the study. Informed consent (Appendix -C) will be collected from both participants and their study partners.

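### The enrollment rate cannot register refusals that come before eligibility screening, so on the natural reading the 80% recruitment target can be met however many women decline at first approach

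*Combined protocol and SAP*

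**What the plan says.** The Statistics section and the objectives table judge feasibility by "comparing the percentages for overall recruitment and retention at week 12 to their target values of 80% and 70%, respectively". A few sentences later both define the rate: "The enrollment rate will be the proportion of those meeting inclusion criteria that enrolled". No other recruitment proportion is defined.

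The order of contact is set in the Recruitment paragraph under Study Population and Eligibility: "staff will explain the study, assess interest in participation, and for those interested, screen for inclusion/exclusion criteria". Eligibility at that stage is preliminary: "Participants will be informed that eligibility will be finalized with the measurement of blood pressure at the in-person baseline visit". Consent then follows eligibility, under Data Collection and Study Procedures: "For participants who are eligible, study staff will describe the study and obtain informed consent".

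Refusals are recorded. The Abstract promises tracking of this kind: "Detailed screening log and record consent rates including refusal reasons". Data and Safety Monitoring adds: "Logs will be maintained of refusals during recruitment". That section also has the team review refusals every two weeks, with IRB notification and changes to recruitment if a worrying trend appears. Data Handling and Record Keeping keeps a complete list of responses to recruitment attempts.

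**The concern.** Recruitment feasibility belongs to the primary objective. The usual question is what share of suitable women, when offered the study, take it up. Here the denominator is formed only after women have said whether they are interested. Those who say no are unscreened, so they cannot be counted as meeting the inclusion criteria.

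The rate therefore describes follow-through among women already interested. A pilot in which most women approached declined could report the same figure as one in which almost all accepted. The Background reports that exercise for oneself is seen by some in this population as selfish or of low priority, so refusal at first offer is a plausible difficulty. The results are meant to support a large efficacy trial, and the number of women to approach is one of its main planning figures.

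**Working it through.** **Figures in the plan.** The 80% target is a set threshold with no derivation to reproduce. The planned sample is 10 dyads, or 10 × 2 = 20 women. The documents give no figures for refusal, eligible share or follow-through, so the values of r, e and c below are assumptions.

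**Step 1: the rate as defined.** Let A be the women approached, r the share refusing before screening, e the share eligible among those screened, and c the share of those found eligible who enroll.

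- Found eligible: A(1 − r)e
- Enrolled: A(1 − r)ec
- Enrollment rate: A(1 − r)ec / A(1 − r)e = c

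The term r cancels, and so does e.

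**Step 2: what the rate does respond to.** Losses after eligibility is known stay in the denominator. Against 20 enrolled:

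- 5 losses: 20/25 = 80.0%, target met
- 6 losses: 20/26 = 76.9%, target missed

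Counted in dyads, 2 losses give 10/12 = 83.3% and 3 give 10/13 = 76.9%.

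**Step 3: chance of meeting 80%.** Suppose recruitment runs until 20 women have enrolled and women act independently. The target is met if at most 5 eligible women are lost before the 20th enrollment:

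P = Σ (k = 0 to 5) C(19 + k, k) c²⁰ (1 − c)ᵏ

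| Assumed follow-through c | P(rate ≥ 80%) |
|---|---|
| 90% | 97% |
| 85% | 84% |
| 80% | 62% |
| 75% | 38% |
| 70% | 19% |

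Neither r nor e appears in the formula. Counting 10 dyads as the units, with at most 2 losses allowed, gives 89% at c = 90%.

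**Step 4: what an uptake rate would show.** Two versions:

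- Scaled: enrolled / (found eligible + refusers × eligible fraction among those screened) = A(1 − r)ec / [A(1 − r)e + Are] = (1 − r)c
- Unscaled, counting every refuser as eligible: (1 − r)ec / [(1 − r)e + r]

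With 20 enrolled, c = 90% and e = 50%, both assumed:

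| Refuse before screening | Approached | Rate as defined | Scaled uptake | Unscaled uptake |
|---|---|---|---|---|
| 0% | 44 | 90% | 90% | 90% |
| 20% | 56 | 90% | 72% | 60% |
| 50% | 89 | 90% | 45% | 30% |
| 80% | 222 | 90% | 18% | 10% |
| 90% | 444 | 90% | 9% | 5% |

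For example, at 50% refusal the scaled version is 0.5 × 0.9 = 45%, and the unscaled version is 0.225/(0.25 + 0.50) = 30%. The scaled version does not depend on e. The unscaled one does: at 50% refusal it is 21%, 30% and 40% for e = 30%, 50% and 80%.

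**The case against.** **The plan does watch refusal.** It logs refusals with reasons and contact methods, reviews them every two weeks and acts on bad trends. A reader might infer that the study would be blind to widespread refusal, and the documents do not support that. What stands is narrower. This monitoring serves conduct and participant protection, and no section carries the logged refusals into the feasibility comparison. The Abstract's consent rates have neither a denominator nor a target. The reach measure under Process Evaluation is worked out as session attendance by dyad members, which comes after enrollment.

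**Refusal is not ignored altogether.** This is correct. Consent follows eligibility, so a woman who declines at consent lowers the rate, and six such losses miss the target. It would be too strong to say that the rate hardly responds to refusal in general, or that refusal at first approach is the main kind. The documents give no refusal figures.

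**The 80% is never expressly tied to the enrollment rate.** Also correct. The link is an inference, though a natural one, since no other recruitment proportion is defined. If the target instead meant 16 of the 20 planned women (0.80 × 20), that figure would not reflect early refusal either.

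**A high chance of passing depends on assumed follow-through.** This stands. At 70% follow-through the chance is about 19%, so it cannot be said that the target would be met regardless.

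**Enrolled over eligible is a legitimate, countable measure, and a denominator of all women approached is only partly observable.** Both points are fair. Women reached by flyer, email list or media leave no individual record. This is a reason to keep the present rate and confine uptake to direct contacts. It is not a reason to let the present rate stand alone as the measure of recruitment.

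**Conclusion.** The point holds for refusal before screening. That the number of early refusers does not affect the rate is arithmetic and follows from the two definitions alone. On the natural reading of the 80% target, recruitment could be declared feasible at any level of early refusal, provided follow-through among interested, eligible women is high. The probability is about 97% at 90% follow-through and falls to 19% at 70%. Those probabilities assume that recruitment stops at 20 enrolled, that women act independently, and that follow-through does not itself change with the level of refusal. The uptake figures assume that refusers are eligible as often as the women screened.

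This is a gap in definition and reporting within the primary objective. The enrollment rate itself is sound for what it measures. The change is worth making because the pilot is meant to inform planning of a larger trial.

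**What to change.** In the Statistics section and the objectives table:

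1. State that the 80% target applies to enrolled divided by eligible, and label that rate *enrollment among interested, screened-eligible women*.
2. From the recruitment logs already planned, report counts of women directly approached, refused before screening, screened, eligible and enrolled.
3. Add an uptake rate: enrolled / (women found eligible + pre-screening refusers × eligible fraction among those screened). Give the version that counts every refuser as eligible as a lower bound.
4. State that meeting 80% alone shows follow-through among interested women, and that the recruitment conclusion and the planning of the next trial will use the uptake rate alongside it.

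The cost is a few sentences and one tabulation, with no added participants or procedures. There are three drawbacks. The recruitment figure becomes less favourable. Uptake covers direct contacts only, not women reached by flyers, email lists or media. The scaling rests on an assumption about refusers' eligibility that cannot be checked, which is why the lower bound should be shown with it.
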